13.2.5 Primary and Secondary Endpoints

Continuous primary and secondary endpoints will be summarized descriptively using the mean (standard deviation), median, minimum, and maximum. Categorical primary and secondary endpoints will be summarized descriptively by frequencies and percentages.

For Cohort I secondary imaging endpoints, agreement comparison analysis between different readers will also be performed. The descriptive statistics including overall, positive and negative percent agreement will be calculated for each endpoint.

For categorical endpoints of Cohort II, the primary analysis will use the number of evaluable radiation dose distributions (Dose Volume Histograms) instead of number of subjects as the denominator under the assumption that all assessments are independent to each other. To evaluate the robustness of the primary analysis results, a sensitivity analysis will be carried out taking the within-subject correlation into account.

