The next two secondary endpoints assess the imaging performance of the PET PreScan. The first of these endpoints seeks to assess the inter-observer agreement for the localization decision made after each RMRS PreScan. A positive or negative decision on the PET PreScan will be indexed against current standard of care for radiotherapy tumor localization: CT-based localization. As such, whether the tumor PET signal is within the BTZ – which is a rigid volume defined on and registered to the patient's CT anatomy – will underpin this determination. The localization decision made by the site investigator will be assessed against an agreement standard made by a panel of independent reviewers using the same RMRS PreScan images with the overlaid BTZ:

2. Percent of cases where there is an agreement between a site investigator and the agreement standard for the BgRT PET PreScan localization decision (overall percent agreement). Positive percent agreement and negative percent agreement will also be reported.

The next imaging secondary endpoint seeks to validate the qualitative visualization of the tumor and OARs on the PreScan against an established reference standard. To establish this concordance, a third-party diagnostic PET/CT scan following the RMRS PET acquisitions obtained prior to the last fraction.

3. Percent of cases where there is concordance of a positive localization decision between the shortduration PET PreScan and a third-party diagnostic PET/CT scan (positive percent agreement). Overall percent agreement and negative percent agreement will also be reported.

Details of these two imaging analyses are described in section 6.3.8 and 6.3.9. Of note, these endpoints will not be limited to only those cases that are evaluable for the primary endpoint. Nonetheless, interpretation of the results of this analysis should bear in mind that the clinically meaningful localization decisions are the positive ones because they would prompt BgRT external beam delivery; negative localization decisions at the RMRS PET PreScan would result in aborting BgRT delivery in clinical practice.

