A fourth secondary endpoint is to measure toxicity arising from multiple administrations of FDG. As described in detail in the IB, the theoretical risk is minimal given first principles of radiation exposure and reassuring animal and human studies of very high-dose FDG administrations. This secondary endpoint will seek to further confirm safety by assessing the organs most likely to be affected by repeat FDG administrations:

4. Safety of multiple FDG administrations and toxicity rates of bladder and bone marrow assessed by complete blood count, urinalysis and AEs specific to bladder and bone marrow determined by Common Terminology Criteria for Adverse Events (CTCAE) v5 at 72±24 hours after final FDG injection.

Finally, characterization of the different steps in the workflow and the robustness of the PET Evaluation pre-delivery will be assessed to better characterize RefleXion system functioning. This data will be collected for all enrolled subjects regardless of the evaluability of their BgRT dose distributions:

- 5. Workflow characterization:
 - a. Percent of PET imaging sessions at RRFD that meet BTZ activation concentration threshold for BgRT (5 kBq/ml)
 - b. Percent of PET imaging sessions that lead to acceptable BgRT plans, with acceptability based upon meeting user-defined coverage goals for tumor targets and avoidance goals for OARs
 - c. Percent of approved BgRT plans that go on to pass physics quality assurance as defined by 90% of pixels meet the 3mm/3% deviation standard.
 - d. Percent of PET PreScan Evaluations on the day of fraction delivery that elicit a "Pass" signal.

For each of these conversion assessments, the constituent metrics underling the outcomes will be recorded. For example, the underlying measurements for the PET PreScan Evaluation (i.e., Activity Concentration, NTS level, predicted DVH, predicted 3D dose distribution, and calculated agreement between the predicted DVH and bounded DVH) will be recorded for each assessment.

Additional exploratory analysis for Cohort II may include pairwise dosimetric comparison of the BgRT and SBRT plans for each lesion. When additional time-paired third-party images are available, they may be compared to RMRS PET images and a qualitative assessment may be performed.

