- 6.3.8.2.5 If reader 1 and reader 2 are in a disagreement, then a third reader who is masked to the first two reads will perform an independent read as a tie breaker. Two agreeing out of the three read results will be selected as the Agreement Standard.
- 6.3.8.3 Inter-observer agreement between the site investigator (SI) and the agreement standard (AS) will be calculated as follows:
 - 6.3.8.3.1 If both SI and AS localization decisions are "yes" then the rating should be "A"
 - 6.3.8.3.2 If SI decides "yes" for localization but AS decides "no" then the rating should be "B".
 - 6.3.8.3.3 If SI decides "no" for localization but AS decides "yes" then the rating should be "C".
 - 6.3.8.3.4 If both SI and AS localizations decisions are "no" then the rating should be "D".
- 6.3.8.4 Based on the rating performed in above section for inter-observer agreement, an overall, positive and negative % agreement will be calculated.

Percent overall agreement = (A+D)/(A+B+C+D) {main analysis}

Percent positive agreement = A/(A+C)

Percent negative agreement = D/(D+B)

6.3.9 Schema for Cohort II Secondary Endpoint #3: RMRS Short-Duration PreScan PET vs. Diagnostic PET Concordance Agreement

6.3.9.1 The comparison of the PET PreScan image after short-duration acquisition and the thirdparty diagnostic PET/CT image will be conducted and descriptive statistics including positive and negative percent agreement will be provided as outlined below.

The positive percent agreement analysis seeks confirmation of RMRS findings in clinically relevant cases based on an affirmative scoring of two questions which qualitatively correspond to a positive localization decision, which is necessary in conjunction with passing quantitative criteria for a PreScan "Pass" signal. For the two questions, FDG-avid targets or organs are defined qualitatively as discrete structures with visually discernable FDG-PET signal above immediate background. The two questions are:

- Q1 (target avidity): Is there an FDG-avid target that correlates to the tumor location on the registered CT image?
- Q2 (confounding non-target signal): Are FDG-avid organs an adequate distance away (≥1 cm) from the FDG-avid tumor for biology-guided radiotherapy?

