13.1.2 Cohort II: Emulated Delivery Cohort

The purpose of Cohort II is to emulate delivery of BgRT plans based upon clinical PET data obtained on the RefleXion system from human subjects using the RRFD established in Cohort I.

The primary endpoint is the percent of radiotherapy fractions where the emulated BgRT dose distribution *in silico* is shown to be consistent with the approved BgRT treatment plan (i.e., 95% of DVH_{Delivered} points for the BTZ and OARs fall within the bounded DVH of the approved BgRT plan).

As previously described in Section 4.3, a BgRT dose distribution is considered evaluable if:

• The subject has successfully undergone BgRT plan creation, physics quality assurance, and plan approval

• A "pass" signal is achieved at the PET PreScan evaluation preceding the long-duration PET emission collection

The sample size was determined a priori to represent a sufficient number of dose distributions for a robust sampling of BgRT deliveries under clinical conditions, including both before and after start of external beam radiotherapy. A sample size of 16 evaluable dose distributions from 8 to 22 subjects will be obtained to inform the concurrence between BgRT dose distributions and approved BgRT plan. Assuming the concurrence rate by the outcomes of primary endpoint follows a binomial distribution, the sample size achieves cumulative probability of approximately 0.81 that at most 1 inconsistency out of 16 evaluable dose distributions when true inconsistency rate is 5%, as shown in below table:

Cumulative Probability at most 1 inconsistency out of 16 evaluable distributions:

True inconsistency rate	40%	30%	20%	10%	5%
Probability at most 1 non- concurrence out of 16 assessments	0.003	0.026	0.141	0.515	0.811

Given that no prior data exists for biology-guided radiotherapy, we will report descriptive statistics for secondary endpoints, as defined in section 4. The summary statistics for BgRT workflow steps will be described for all enrolled patients including those with non-evaluable dose distributions.

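### Section 13.2.5 sets evaluable dose distributions as the denominator for Cohort II categorical endpoints without exception; this contradicts 4.3, 13.1.2 and the agreement formulas and, read literally, fixes the PreScan pass rate at 100%

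*Combined protocol and SAP*

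**What the plan says.** Section 13.2.5, whose heading covers primary and secondary endpoints, sets the rule: "For categorical endpoints of Cohort II, the primary analysis will use the number of evaluable radiation dose distributions" as denominator in place of the number of subjects. It treats the assessments as independent and adds a sensitivity analysis for within-subject correlation. A parenthesis glosses the distributions as dose volume histograms. No endpoint is excepted.

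Section 13.1.2 gives two conditions for an evaluable distribution. The first is "The subject has successfully undergone BgRT plan creation, physics quality assurance, and plan approval". The second is that a pass "signal is achieved at the PET PreScan evaluation preceding the long-duration PET emission collection".

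Other sections define the secondary endpoints on wider sets:

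- **Imaging endpoints 2 and 3.** Section 4.3 says "these endpoints will not be limited to only those cases that are evaluable for the primary endpoint". The main analysis of endpoint 2 in 6.3.8.4 is "Percent overall agreement = (A+D)/(A+B+C+D) {main analysis"; that of endpoint 3 in 6.3.9.6 is A/(A+C). Both count reads.
- **Workflow endpoints 5a to 5d.** Section 4.3 says "This data will be collected for all enrolled subjects regardless of the evaluability of their BgRT dose distributions". Section 13.1.2 makes the same point about analysis: "The summary statistics for BgRT workflow steps will be described for all enrolled patients including those with non-evaluable dose distributions".

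**The concern.** The evaluable-distribution denominator suits the primary endpoint and secondary endpoint 1. Both concern emulated dose distributions, and 4.3 deliberately limits those analyses to fractions at which BgRT would have been delivered. Applied to the other categorical endpoints, the same denominator selects on success. A distribution becomes evaluable only after the plan has been created, has passed quality assurance and has been approved, and after the PreScan has passed. A rate meant to show how often those steps succeed then loses its failures.

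Endpoint 5d is the clearest case. Section 1.3.3 presents the PreScan evaluation as the safety interlock before beam-on, and 5d summarises how often it passes. A programmer working from 13.2.5 and one working from 13.1.2 would produce different tables for it, and the protocol does not say which sentence takes precedence.

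**Working it through.** **Inputs.** 16 evaluable distributions from 8 to 22 subjects (13.1.2). PreScan collections are planned before the first and final SBRT fractions, and one diagnostic PET/CT per subject is planned (4.3). An approved BgRT plan must exist before the fraction collections (6.3.5). After a failed PreScan the investigator may repeat FDG at a later fraction, and further subjects may be accrued (4.3). No expected number of failed PreScans is given, so f below is an assumption.

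**The plan's own figure.** P(at most 1 inconsistency in 16) = (1−p)^16 + 16p(1−p)^15. At p = 5% this is 0.440 + 0.371 = 0.811, as stated. At 40, 30, 20 and 10% it gives 0.0033, 0.0261, 0.1407 and 0.5147, matching 0.003, 0.026, 0.141 and 0.515. The table is correct and is not at issue.

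**Endpoint 5d.** Every PreScan follows an approved plan, so each pass with a completed long-duration collection is an evaluable distribution. With 16 of these and f fails:

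| f (assumed) | Literal 13.2.5 | All PreScans, 16/(16+f) |
|---|---|---|
| 0 | 16/16 = 100% | 16/16 = 100% |
| 2 | 16/16 = 100% | 16/18 = 88.9% |
| 4 | 16/16 = 100% | 16/20 = 80.0% |
| 8 | 16/16 = 100% | 16/24 = 66.7% |
| 16 | 16/16 = 100% | 16/32 = 50.0% |

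The middle column is the same whether the rule is read as restricting the cases or only as setting the divisor. One edge case remains: a pass without a usable long-duration collection would take the divisor-only ratio above 100%.

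**Endpoints 5a to 5c.** Counted per evaluable distribution, each is 16/16 by construction. Plan creation, quality assurance and approval are conditions of evaluability (13.1.2), and 6.2.2 requires the Activity Concentration threshold for a successful plan. Counted instead as sessions or plans over 16 distributions, the units do not match. Eight subjects, each with one successful session and two distributions, would give 8/16 = 50% although every session succeeded.

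**Endpoint 3.** With one planned diagnostic scan per subject, perfect concordance over a divisor of 16 would read 8/16 = 50% for 8 subjects and 22/16 = 137.5% for 22. The 6.3.9.6 formula gives 100% in both cases.

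**Endpoint 2, conditional.** If a Pass includes a positive localization decision, as 6.3.9.1 says, no evaluable case has a site read of No, so C = D = 0. Positive agreement is then A/(A+0) = 100%, and negative agreement is 0/(0+B) = 0%, or undefined if B = 0. Take assumed counts A = 15, B = 1, C = 1, D = 3, with the 16 site reads of Yes being the evaluable cases:

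| | All reads | Evaluable only |
|---|---|---|
| Overall | 18/20 = 90.0% | 15/16 = 93.8% |
| Positive | 15/16 = 93.8% | 15/15 = 100% |
| Negative | 3/4 = 75.0% | 0/1 = 0% |

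If Pass is only the quantitative signal, C and D need not be zero and this result does not follow.

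**The case against.** The strongest reply is that the specific text already settles the populations. Section 13.1.2, in the same statistical chapter, covers the workflow endpoints for everyone enrolled, and it says "we will report descriptive statistics for secondary endpoints, as defined in section 4", which points back to the definitions in 4.3. The agreement formulas are exact. Endpoint 5d names its own denominator, the PET evaluations. The histogram gloss in 13.2.5, and its contrast with counting subjects, suggest that the author meant only to set the unit for the dose-distribution endpoints. The plural endpoints would be satisfied by the primary endpoint and secondary endpoint 1 alone. Section 13.3 also leaves room for the SAP to differ. Most of this stands, and it lowers the impact. It does not remove the contradiction: the sentence has no limiter, no order of precedence is given, and no SAP text in the documents resolves it.

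A reader might infer more than the documents support:

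- **That failed PreScans would vanish from the report.** Section 4.3 records the underlying measurements for each assessment, and 13.2 plans patient data listings. The summary rate is at risk, not the record.
- **That endpoint 2 is necessarily degenerate on evaluable cases.** Section 6.3.9.1 supports that, but 6.3.5 ties pass or fail to quantitative measures, and 1.3.3 treats visual localization as a separate condition. The result is conditional.
- **That toxicity rates would be divided by histogram counts.** Safety has its own section, 13.2.4, and nothing in 13.2.5 indicates that it is displaced.
- **That endpoint 5c needs redefining.** Its stated denominator, approved plans, is usable; the order of approval and quality assurance is a separate question.

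**Conclusion.** The point holds as a wrong stated rule with limited consequences. As written, 13.2.5 conflicts with 4.3 and the formulas in 6.3.8.4 and 6.3.9.6 for endpoints 2 and 3, and with 4.3 and 13.1.2 for endpoints 5a to 5d. The firmest result is 5d: the literal rule returns 100% whatever the number of fails, where all PreScans would give 80% or 67% at f = 4 or 8. That the literal rate is constant follows from the evaluability conditions, given a completed long-duration collection after each pass. The size of the gap depends entirely on f, which the documents do not predict.

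A reader might also infer that the primary result or the sample size is compromised. Neither is: the evaluable denominator is the intended one there, and the binomial table reproduces. All the affected endpoints are descriptive. The correction should be made before the tables are programmed, but it does not bear on the trial's main conclusion.

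**What to change.** In 13.2.5, or in the SAP that 13.3 says is finalised before database lock:

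- Limit the evaluable-distribution denominator to the primary endpoint and secondary endpoint 1.
- For endpoints 2 and 3, refer to the formulas in 6.3.8.4 and 6.3.9.6, applied to all cases read regardless of evaluability. The main analysis of endpoint 3 stays A/(A+C).
- For 5a to 5d, use the denominators already in the endpoint wording, over all enrolled subjects: PET imaging sessions for 5a and 5b, approved BgRT plans for 5c, and all PreScan evaluations, including fails and repeats, for 5d.
- Keep the within-subject-correlation sensitivity analysis for endpoints with more than one observation per subject (the primary endpoint, endpoints 1 and 2, and 5d).

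The cost is a few sentences. Data collection, the primary endpoint and the 16-distribution table do not change. The price to the sponsor is that some reported rates, 5d above all, may be less favourable than under the literal rule.

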To that end, the fluence resulting from the hardware instruction set will be delivered into a physical phantom in order to emulate delivery during BgRT. The dose and distribution measured in the phantom will be judged against *in silico* delivery of the same instruction set to a digital facsimile of the phantom, as per standard physics quality assurance methodology.

As such, the first secondary endpoint will be the following:

1. Percent of fractions where there is concordance between the physical and digital phantoms of emulated BgRT delivery derived from human subject PET emissions. Concordance is defined as a standard gamma index with a goal that 90% of pixels meet the 3mm/3% deviation standard.

Collectively, these primary and secondary analyses emulate end-to-end BgRT delivery insofar as they enable visualization of anatomic dose distributions resulting from varying PET LTS conditions and confirm quality assurance and delivery of those dose distributions by the linear accelerator hardware. In this way, these analyses address the known limitation of human subjects research in radiotherapy device validation (see section 1.5), which is that dose distributions are not directly measurable *in vivo*.

[figure not shown]

Figure 7. Physical and Dosimetric Validation of BgRT Plan Delivery Based upon Human-Subject Derived PET Data on the RefleXion System

To reflect clinical conditions, these analyses of BgRT dose distribution are necessarily limited to those fractions where BgRT would have been delivered in practice. Therefore, a dose distribution is evaluable for the primary endpoint if, preceding the long-duration PET collection, (1) an acceptable BgRT plan was approved and (2) the PET PreScan evaluation delivered a "Pass" signal. In order to obtain a total of 16 evaluable dose distributions for assessing delivery quality in Cohort II, a minimum of 8 subjects (4 bone tumors and 4 lung tumors) and up to 22 subjects can be accrued. For an enrolled subject, if a PET PreScan delivers a "Fail" signal prior to long-duration PET collection, then the investigator can choose to repeat FDG administration at a subsequent treatment fraction for that subject (which again reflects clinical practice). If a data point is ultimately non-evaluable, then an additional patient with the same anatomic type of tumor can be accrued. Once a total of 16 evaluable dose distributions are acquired, Cohort II accrual will stop.

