13.3 Statistical Analysis Plan

The Statistical analysis plan (SAP) will be finalized prior to database lock. Any analysis that is different than what is in the protocol will be described in detail in the SAP.

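### Does the Cohort II primary percentage need a prespecified interval and a named within-subject method, given that 16 distributions may be 8 pairs?

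*Combined protocol and SAP*

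**What the plan says.** Section 13.2.5 sets the form of reporting: "Categorical primary and secondary endpoints will be summarized descriptively by frequencies and percentages". For Cohort II the denominator is evaluable dose distributions rather than subjects, "under the assumption that all assessments are independent to each other". It then adds that "a sensitivity analysis will be carried out taking the within-subject correlation into account". It gives no confidence level, interval, model or variance method.

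Section 13.1.2 sets the size: "A sample size of 16 evaluable dose distributions from 8 to 22 subjects will be obtained". Its justification begins "Assuming the concurrence rate by the outcomes of primary endpoint follows a binomial distribution" and concludes that the "sample size achieves cumulative probability of approximately 0.81 that at most 1 inconsistency out of 16 evaluable dose distributions" at a true inconsistency rate of 5%.

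Section 4.3 gives the possible cluster structure. Collections are taken before the first and the final SBRT fraction, "a minimum of 8 subjects (4 bone tumors and 4 lung tumors) and up to 22 subjects can be accrued", and accrual ends once 16 evaluable distributions are in hand. Section 6.3.7 checks each emulated distribution against the bounded DVH of the approved BgRT plan.

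Section 13.3 says: "The Statistical analysis plan (SAP) will be finalized prior to database lock". No finalized SAP is in the supplied text.

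**The concern.** If the first 8 subjects are all fully evaluable, the 16 results are 8 pairs. The two members of a pair share a tumor, an anatomy and one approved plan, so correlation is plausible. The true information would then lie between that of 8 and that of 16 independent observations. A bare 100% or 93.75% does not show this, and an interval computed at n = 16 would be too narrow.

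The unnamed method adds to the worry. The design is built around seeing 0 or 1 inconsistency, and at 16/16 several standard clustered methods break down. A cluster bootstrap has zero width because every resample is 16/16. A logit GEE has no finite estimate, and the correlation cannot be estimated. The promised robustness check could then be uninformative for the result the sponsor hopes to see. At stake is how much weight a near-perfect result from perhaps 8 people can bear.

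**Working it through.** **Inputs.** 16 distributions, a minimum of 8 subjects and two fractional collections per subject (sections 4.3 and 13.1.2). The documents give no ICC and no confidence level, so ICC from 0 to 1 and a two-sided 95% level are assumptions.

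**1. The plan's table.** With X ~ Binomial(16, p), P(X ≤ 1) is 0.0033, 0.0261, 0.1407, 0.5147 and 0.8108 at p = 40%, 30%, 20%, 10% and 5%. The stated values are 0.003, 0.026, 0.141, 0.515 and 0.811. All five reproduce.

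**2. The table under pairing.** For 8 pairs with ICC ρ and q = 1 − p, let P00 = q² + ρpq and P1 = 2pq(1 − ρ). Then P(X ≤ 1) = P00⁸ + 8·P00⁷·P1.

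| True rate | ρ = 0 | ρ = 0.25 | ρ = 0.5 |
|---|---|---|---|
| 5% | 0.811 | 0.793 | 0.764 |
| 10% | 0.515 | 0.530 | 0.526 |
| 20% | 0.141 | 0.175 | 0.201 |
| 30% | 0.026 | 0.042 | 0.060 |

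The probability falls at 5% and rises at 10% and above. The shifts are modest and their direction depends on the rate. At ρ = 1 and 5% it is 0.663, but part of that drop is parity: with fully correlated pairs exactly one inconsistency cannot occur, while P(0) rises from 0.440 to 0.663.

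**3. Precision of the result.** Effective n with 8 pairs is 16/(1 + ρ). The Clopper-Pearson lower 95% limit at 16/16 is 0.025^(1/n). At 15/16 it is the 2.5% quantile of Beta(15n/16, n/16 + 1).

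| ρ | Effective n | 16/16 | 15/16 |
|---|---|---|---|
| 0 | 16 | 79.4% | 69.8% |
| 0.25 | 12.8 | 75.0% | 65.6% |
| 0.5 | 10.67 | 70.8% | 61.7% |
| 1 | 8 | 63.1% | 54.6% |

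The 54.6% is a formula bound only, since an odd count cannot arise from 8 pairs at ρ = 1. With 12 subjects (4 pairs, 8 singles) the effective n is 16/(1 + ρ × 8/16). The 16/16 limits are then 79.4%, 77.2%, 75.0% and 70.8% at the same four values of ρ. With 16 single distributions the limit is 79.4% at any ICC.

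**4. Where an n = 16 limit undercovers.** Exact enumeration with 8 pairs, over inconsistency rates from 0.5% to 60%, gives minimum coverage of the lower limit (nominal 97.5%) of 95.9%, 93.4% and 84.2% at true ICC 0.25, 0.5 and 1. All three minima occur at a rate of about 20.6%, just past 1 − 0.794, where the 16/16 limit first misses the true value. Coverage there is 1 − P00⁸; at ρ = 1 this is 1 − 0.794⁸ = 0.842. At rates from 0.5% to 20.5% the limit covers every time, whatever the ICC, because even a perfect result has a lower limit below the truth.

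**The case for a change.** The best case for a change is that 16/16 is a likely outcome: its probability at a 5% rate is 0.440 under independence and higher with correlation. A primary result of 100% from possibly 8 people, with no interval, leaves unsaid a lower limit somewhere between about 63% and 79%. The study is open-label and section 13.3 commits to no particular method, so the choice could be made after the results are seen. A few lines of text would settle it at no cost in patients.

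Much of this stands as fact. The interval is not stated, the method is not named, and a careless choice would give an empty sensitivity analysis at 16/16. It does not show a defect in the plan. The within-subject problem was recognised and an analysis for it promised; only the estimator is open, and the SAP is the usual place for it. An analyst meeting 16/16 would see at once that a bootstrap or GEE is unusable and turn to an exact calculation at a reduced effective n, or to a per-subject summary. With no success threshold, choosing the method late gains nobody a favourable decision. Section 13.2 also promises patient data listings, so a reader who has the count can compute an exact interval, and can judge the pairing if the listings show each fraction.

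**Conclusion.** This is a gap in detail that analysts can fill sensibly, and the plan need not change. The independence assumption is declared, a correlation-adjusted analysis is committed to, the table in section 13.1.2 is right on its own terms, and neither a decision nor the point estimate turns on the method.

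The size of the effect is a matter of precision: at most 79.4% down to 63.1% for the lower limit at 16/16, and only if all 16 results are pairs with complete correlation. That extreme is unlikely. The two collections are separated in time, and both must first pass the PreScan check against the same bounded DVH, which may lower the correlation. More subjects with single distributions shrink the effect, to nothing if all 16 are singles. The table does not need to be redone.

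The conclusion rests on the assumed ICC range and 95% level, and on the endpoint remaining descriptive. Whether the finalized SAP names a method cannot be checked from the documents supplied.
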